## 6 TREATMENT

The investigational drug will be BGJ398 as an oral formulation (hard gelatin capsules).

# 6.1 Study treatment

The pharmacist will dispense the correct number and dose strength of capsules to ensure that each patient receives sufficient drug until the next scheduled visit.

## 6.1.1 Dosing regimen

Table 3: Dose and treatment schedule

Study treatment	Formulation	Pharmaceutical form and route of administration	Dose	Frequency and/or Regimen
BGJ398	FMI I	Hard gelatin capsule(s) for	125 mg	Daily (3 weeks on,
	FMI III FMI IV	oral use	(administered as one 100 mg capsule and one 25 mg capsule)	1 week off schedule in 28-day cycles)

## 6.1.1.1 Instructions for administration of BGJ398

- Patients should be instructed to take the daily dose of BGJ398 in the morning, at approximately the same time each day (24 ± 4 hour interval). Patients will take their first dose of infigratinib at the study center on Cycle 1 Day 1. On the days of PK sampling, patients should not take their study drug dose at home; patients should take their study drug with them to the investigative site where administration of BGJ398 will be supervised and administration time recorded. On PK sampling days after Cycle 1 Day 1, the time of the previous infigratinib administration (ie, the prior day) before the pre-dose PK sample will be recorded in the eCRF. Administration may fall outside of the ±4 hour interval on the days of PK sampling.
- Patients who initiate treatment as of the implementation of amendment 2 will begin treatment using the FMI III form of BGJ398; patients enrolled into Cohorts 2 and 3 under amendment 4 will receive the FMI IV form of BGJ398. Patients who started treatment prior to the implementation of amendment 2 should continue to receive the formulation of BGJ398 that they received at the initiation of treatment until FMI IV is available at the study site. At that time all patients on study will receive FMI IV.
- BGJ398 should be administered in the fasted state at least 1 hour before or 2 hours after a meal.
- BGJ398 should be taken with a large glass of water (~250 mL) and consumed over as short a time as possible. Patients should be instructed to swallow the capsules whole and not chew them.
- If the patient forgets to take the scheduled dose in the morning (other than on a day of PK sampling), he/she should not take the dose more than 4 hours after the usual time and should continue treatment the next day. Any such doses that are missed should be skipped altogether and should not be replaced or made up at the next scheduled dosing.
- If vomiting occurs following the dosing of study drug, re-dosing is not permitted that same day. Dosing should resume the next day. If the vomiting occurs on full PK sampling days within the first 4 hours post-dosing, this event needs to be noted on the dose administration PK eCRF page, as well as on the adverse event page, as appropriate.
- BGJ398 is characterized by pH-dependent solubility, and therefore, medicinal products that alter the pH of the upper gastro-intestinal tract may alter the solubility of BGJ398, and limit bioavailability. These agents include, but are not limited to, proton pump inhibitors (eg, omeprazole), H2-antagonists (eg, ranitidine) and antacids. If possible, proton pump inhibitors should be avoided due to their long pharmacodynamic effect and replaced with H2-antagonists or antacids. BGJ398 should be dosed at least 2 hours before or 10 hours after dosing with a gastric protection agent.

- Patients must avoid consuming grapefruits, grapefruit juice, grapefruit hybrids, pomegranates, star fruits, pomelos, Seville oranges, or products containing juice of these fruits, within 7 days prior to the first dose of study medication, through the end of study participation. This is due to a potential CYP3A4 interaction with study
- The investigator or responsible site personnel should instruct the patient to take the study drug exactly as prescribed to promote compliance. All dosages prescribed and dispensed to the patient and all dose changes or missed doses during the study must be recorded on the Dosage Administration Record eCRF.

medication. Normal oranges and orange juice are allowed.

Drug accountability must be performed on a regular basis. Patients will be instructed
to return unused study drug to the site at the end of each cycle. The site personnel will
ensure that the appropriate dose of each study drug is administered at each visit and
will provide the patient with the correct amount of drug for subsequent dosing.

# 6.1.2 Ancillary treatments

Phosphate-lowering treatment, including low phosphate diet and phosphate binding therapy such as sevelamer hydrochloride, should be implemented prophylactically with meals on the first day of study drug initiation and modified as clinically indicated throughout BGJ398 administration. Recommendations for treatment are provided in Table 5, but should be modified as per country or institutional guidelines.

### 6.1.3 Treatment duration

All patients will receive BGJ398 daily on a three week on (21 days), one week off (7 days) schedule in 28-day cycles. Patients may continue treatment with BGJ398 until the patient experiences unacceptable toxicity, disease progression, treatment is discontinued at the discretion of investigator or withdrawal of consent, or death.

## 6.2 Dose modifications

# 6.2.1 Dose modifications and dose delay

For patients who do not tolerate the protocol-specified dosing schedule, dose adjustments are permitted in order to allow the patient to continue the study treatment. All dose modifications should be based on the worst preceding toxicity (Table 5, Table 6). Dosage changes must be recorded on the Dosage Administration Record CRF.

The following guidelines should be applied.

Each patient will be allowed 3 dose reductions according protocol-specified dose modifications for AEs. A QED medical monitor or designee approval is required for the third dose reduction (Table 4).

Following resolution of toxicity to baseline or  $\leq$  Grade 1, treatment is resumed at either the same or lower dose of study drug as per the criteria in Table 5. If treatment is

resumed at the same dose of study drug, and the same toxicity recurs with the same or worse severity regardless of duration, dose must be reduced to the next lower dose level. If treatment is resumed at the lower dose of study drug, and the same toxicity recurs with the same or worse severity, the patient should have a second dose reduction.

Patients who discontinue study treatment for a study related adverse event or an abnormal laboratory value must be followed as described in Section 6.2.2.

Study drug must be permanently discontinued for a delay of >14 days and may only be restarted with written permission of a QED Therapeutics' medical monitor if (1) the delay was not due to an AE that requires permanent study drug discontinuation as provided in Table 5, and (2) the patient has not met other criteria requiring study drug discontinuation in Section 7.1.4, and it is the Investigator's opinion that no safety concerns are present.

Table 4: Dose reduction table

Dose reduction				
	Starting dose level 0	Dose level -1	Dose level -2	Dose level -3
BGJ398	125 mg	100 mg	75 mg	50 mg a

Dose reduction to 50 mg requires QED Therapeutics medical monitor approval. Details are provided in the text above.

 Table 5:
 Criteria for interruption and re-initiation of BGJ398 treatment

Worst Toxicity CTCAE v4.03 Grade (unless otherwise specified)	Dose Modifications any time during a cycle of therapy
Cardiac disorders	
Cardiac - Prolonged QTcF interval	
Grade 1 and 2: QTcF ≥ 481 msec and ≤ 500 msec (asymptomatic)	
 
Maintain dose level of BGJ398         Two additional electrocardiograms (ECGs) separated by at least 5 minutes should be performed to confirm the finding. If the finding is confirmed, single ECG assessments should be performed for 2 additional cycles at the same frequency as in cycle 1, or as clinically indicated. If abnormality is detected, 2 additional ECGs separated by at least 5 minutes should be performed to confirm the finding.         
 
If ECG assessments show no QTcF ≥ 481 msec, for subsequent cycles ECG monitoring will be performed as per the visit schedule.
 
If ECG assessments are still abnormal (QTcF ≥ 481 msec and ≤500 msec), then ECG monitoring must continue at the same frequency as in cycle 1 for all subsequent cycles.
 

Grade 3: QTcF > 500 msec as identified on the ECG by the investigator	
 
Hold BGJ398. Two additional ECGs separated by at least 5 minutes should be performed to confirm the finding. If the finding is confirmed, monitor patient with hourly ECGs until the QTcF has returned to baseline and perform further monitoring as clinically indicated.
 
Exclude other causes of QTcF prolongation such as hypokalemia, hypomagnesaemia and decreased blood oxygenation.
 
Patients should receive appropriate electrolyte replacement and should not receive further BGJ398 until electrolytes are documented to be within normal limits.
 
Once the QTcF prolongation has resolved, patients may be re-treated at one lower dose level at the investigator's discretion
 
Single ECG assessments should be performed for 2 additional cycles at the same frequency as in cycle 1 or as clinically indicated. If abnormality is detected, 2 additional ECGs separated by at least 5 minutes should be performed to confirm the finding.
 
If ECG assessments show no QTcF ≥ 481 msec, ECG monitoring will be performed as per the visit schedule for subsequent cycles.
 

Worst Toxicity CTCAE v4.03 Grade (unless otherwise specified)	Dose Modifications any time during a cycle of therapy
	
 
If ECG assessments are still abnormal (QTcF ≥ 481 msec and ≤500 msec), then ECG monitoring must continue at the same frequency as in cycle 1 or as clinically indicated, for all subsequent cycles
 
Patients who experience recurrent QTcF ≥ 500msec after one dose reduction will be discontinued from study treatment.
 

Grade 4: QTcF >500 or >60 msec change from baseline and Torsade de pointes or polymorphic ventricular tachycardia or signs/symptoms of serious arrhythmia	Discontinue BGJ398.  If QTcF >500 msec or >60 msec change from the baseline is observed, a plasma
of serious arring tilling	sample for determination of BGJ398 concentration should be obtained with the time of sample collection noted.
Cardiac disorders - others	
Grade $\geq 3$ , or congestive heart failure $\geq 2$	Discontinue patient from study treatment.
Investigations-Hematology	
Neutrophil count decreased (Neutropenia)	
Grade 3 (ANC < 1.0 - 0.5 x 10  /L)	
 
Hold dose of BGJ398 until resolved to CTCAE Grade ≤ 1 or baseline, then
 
If resolved within ≤ 7 days, maintain dose level of BGJ398.
 
If resolved between > 7 days and 14 days, ↓ 1 dose level of BGJ398.
 
If not resolved within ≤14 days, discontinue patient from study treatment.
 

Grade 4 (ANC < 0.5 x 10  /L)	Hold dose of BGJ398 until resolved to CTCAE ≤ Grade 1, ↓ 1 dose level of BGJ398.  If not resolved within ≤14 days, discontinue patient from study treatment.
Febrile neutropenia	
Grade 3 (ANC < 1.0 x $10^9$ /L, single temperature of > 38.3°C or a sustained temperature of $\ge 38.0$ °C)	Hold dose of BGJ398 until resolved to CTCAE Grade ≤ 1, then  If resolved within ≤ 7 days, ↓ 1 dose level of BGJ398.  If not resolved within 7 days discontinue patient from study drug treatment.
Grade 4	Discontinue patient from study treatment.
Anemia	
Grade 3 (hemoglobin <8.0 mg/dL)	Hold dose of BGJ398 until resolved or corrected to CTCAE Grade ≤ 1 or baseline, then maintain dose level
Grade 4	Hold dose of BGJ398 until resolved or corrected to CTCAE Grade ≤ 1 or baseline, then ↓ 1 dose level

Worst Toxicity CTCAE v4.03 Grade (unless otherwise specified)	Dose Modifications any time during a cycle of therapy
Platelet count decreased (Thrombocytopenia)	
Grade 3 (platelet < 50 - 25 x 10  /L ) without Grade ≥2 bleeding	
 
Hold dose of BGJ398 until resolved to CTCAE Grade ≤ 1 or baseline
 
If resolved within ≤ 7 days, maintain dose level of BGJ398.
 
If resolved between > 7 days and 14 days, ↓ 1 dose level of BGJ398
 
If not resolved within ≤14 days, discontinue patient from study treatment.
 

Grade 3 (platelet $<$ 50 - 25 x 10 $^9$ /L ) with Grade $\ge$ 2 bleeding or Grade 4 (platelet $<$ 25 x 10 $^9$ /L )	Hold dose of BGJ398 until resolved to CTCAE Grade ≤ 1 or baseline, then ↓ 1 dose level.  If not resolved within ≤14 days, discontinue patient from study treatment.
Investigations – Renal	
Serum creatinine	
Creatinine clearance <45 mL/min (calculated or measured)	Hold BGJ398 until creatinine clearance is ≥45 mL/min regardless of grade.
Serum creatinine Grade 2 (≥1.5 - 3.0 x ULN or 1.5-3.0 × baseline)	Hold dose of BGJ398 until resolved to Grade ≤1 or baseline:  If resolved within ≤ 7 days, maintain dose level of BGJ398.  If resolved between > 7 days and 14 days, ↓ 1 dose level of BGJ398.  If not resolved within ≤14 days, discontinue patient from study treatment.
Serum creatinine Grade ≥2	If serum creatinine CTCAE Grade $\geq 2$ has been demonstrated in conjunction with hyperphosphatemia, serum creatinine levels must be repeated at least weekly until resolution. 24-hour urine collection should be obtained as clinically indicated for total phosphate, calcium, protein, and creatinine clearance. Ultrasound examination of the kidneys should be performed as indicated to evaluate $de$ -novo calcifications until resolution or stabilization of creatinine.
Serum creatinine Grade $\geq 3$ (> 3.0 x ULN or >3 × baseline)	Discontinue patient from study treatment.
Investigations – Hepatic	
Blood bilirubin (for patients with Gilbert Syndrome, these dose modifications apply to changes in direct bilirubin only)	
Grade 2 (> 1.5 - 3.0 x ULN)	
 
Hold dose of study drug until resolved to CTCAE Grade ≤ 1
 
If resolved within ≤ 7 days, maintain dose level of BGJ398.
 
If not resolved within ≤ 7 days, ↓ 1 dose level of BGJ398
 

Grade ≥3 (> 3.0 x ULN)	Discontinue patient from study treatment.

Worst Toxicity CTCAE v4.03 Grade (unless otherwise specified)	Dose Modifications any time during a cycle of therapy
	Note: If CTCAE Grade 3 or 4 hyperbilirubinemia is due to hemolysis, then ↓ 1 dose level of BGJ398 and continue treatment at the discretion of the Investigator.
AST or ALT	
Grade 3 (> 5.0 - 20.0 x ULN) without bilirubin elevation > 2.0 x ULN	
 
Hold dose of BGJ398 until resolved to CTCAE Grade ≤ 1 or baseline
 
If resolved within ≤ 7 days, ↓ 1 dose level of BGJ398.
 
If not resolved within ≤ 7 days, discontinue patient from study treatment.
 

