Grade ≥ 2	Discontinue patient from study drug treatment
Diarrhea	
General Comment	Antidiarrheal medication is recommended at the first sign of abdominal cramping, loose stools or overt diarrhea
Grade 1	Maintain dose level of BGJ398, initiate anti-diarrheal treatment
Grade 2	
 
Hold dose of BGJ398 until resolved to CTCAE Grade ≤ 1
 
Optimize anti-diarrheal treatment.
 
For reoccurrence of diarrhea CTCAE Grade 2, hold dose of BGJ398 until resolved to CTCAE Grade ≤ 1, ↓ BGJ398 by 1 dose level
 

Grade 3	
 
Hold dose of BGJ398 until resolved to CTCAE Grade ≤ 1
 
Optimize anti-diarrheal treatment
 
↓ BGJ398 by 1 dose level
 
For reoccurrence of diarrhea CTCAE Grade 3, despite optimal antidiarrheal treatment, discontinue patient from study treatment.
 

Grade 4	Discontinue patient from study treatment.
Vomiting	
Grade 2 not controlled by optimal anti-emetic therapy	Hold BGJ398 doses until ≤ Grade 1, ↓ 1 dose level.

Worst Toxicity CTCAE v4.03 Grade (unless otherwise specified)	Dose Modifications any time during a cycle of therapy
	If not resolved within ≤14 days, discontinue patient from study treatment.
Grade 3 not controlled by optimal anti-emetic therapy or Grade 4	Discontinue patient from study treatment.
Eye Disorders (confirmed by ophthalmic examination)	
Retinal disorders	
Grade 2 central serous retinopathy and central serous retinopathy - like events	Hold BGJ398 until resolved to ≤ Grade 1 and continue ophthalmic evaluation  • If resolved within ≤ 14 days, ↓ BGJ398 by 1 dose level  • If resolved after > 14 days, discontinue BGJ398
Grade 3 central serous retinopathy and central serous retinopathy- like events and any other Grade 3 eye disorders	Hold BGJ398 until resolved to Grade ≤ 1.  If resolved within ≤ 14 days, ↓ BGJ398 by 1 dose level  If resolved after > 14 days, discontinue BGJ398
≥ Grade 1 retinal vein occlusion, Grade 4 central serous retinopathy and central serous retinopathy-like events, and Grade 4 other eye disorders	Discontinue patient from study treatment.
Other ocular/visual toxicity	
≥ Grade 3	Hold BGJ398 until resolution to ≤ Grade 1
	• If resolution within ≤14 days, ↓ 1 dose level
	• If resolved after >14 days, discontinue BGJ398
General disorders	
Fatigue	
Grade ≥3	Hold dose of BGJ398 until resolved to CTCAE Grade ≤ 1
	• If resolved within ≤ 7 days, maintain dose level of BGJ398.
	• If resolved after > 7 days, discontinue patient from study treatment.

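### Section 6.2.1 prescribes a second dose reduction for a toxicity that recurs at the lower dose, while Table 5 requires stopping in two such cases, and no text says which rule governs

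*Protocol*

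**What the plan says.** Protocol Section 6.2.1 gives two general recurrence rules. They follow the statement that treatment resumes at the same or a lower dose by the Table 5 criteria.

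- Resumed at the same dose: if "the same toxicity recurs with the same or worse severity regardless of duration, dose must be reduced to the next lower dose level".
- Resumed at a lower dose: if "the same toxicity recurs with the same or worse severity, the patient should have a second dose reduction".

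Neither sentence names an exception. The section allows three reductions per patient and requires medical monitor (or designee) approval for the third. Table 4 sets the levels at 125, 100, 75 and 50 mg.

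Table 5 then gives row-specific rules. For Grade 3 QTcF prolongation (above 500 msec), the first event leads to a hold and then "Once the QTcF prolongation has resolved, patients may be re-treated at one lower dose level", at the investigator's discretion. On recurrence: "Patients who experience recurrent QTcF ≥ 500msec after one dose reduction will be discontinued from study treatment". For Grade 3 diarrhea, the first event leads to a hold, optimized antidiarrheal treatment and a one-level reduction. On recurrence: "For reoccurrence of diarrhea CTCAE Grade 3, despite optimal antidiarrheal treatment, discontinue patient from study treatment".

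**The concern.** In both rows the first event puts the patient on a lower dose, which is the condition for the second-reduction sentence in Section 6.2.1. If the same event recurs at the same severity, that sentence keeps the patient on drug one level down, while the Table 5 row takes the patient off drug. The Glossary defines study treatment discontinuation as a permanent stop, so the two instructions cannot both be followed.

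The possible error runs in the less cautious direction: a patient could be re-dosed after a second QTcF above 500 msec. Consistent conduct across sites is also at stake. Section 12 permits no authorized deviations, and SAP Section 2.4 counts a patient who met withdrawal criteria but was not withdrawn as a reportable deviation. A site that followed Section 6.2.1 literally could be recorded as deviating.

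**Working it through.** No figure in the plan needs reproducing. The check compares each recurrence instruction in Table 5 with Section 6.2.1, and then looks for text that settles precedence.

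**Step 1. Recurrence instructions in Table 5.** There are four.

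| Row | Table 5 on recurrence | Section 6.2.1 | Result |
|---|---|---|---|
| Grade 3 QTcF, after one reduction | Discontinue | Second reduction | Conflict |
| Grade 3 diarrhea, despite optimal treatment | Discontinue | Second reduction | Conflict |
| Grade 3 lipase/amylase, despite reduction | Hold; discuss continuation with the monitor | Second reduction | Differs, but not a mandatory stop |
| Grade 2 diarrhea | Hold, then reduce one level | Reduce (same-dose rule) | Agrees |

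Two of four conflict outright, one differs and one agrees. The QTcF row is triggered above 500 msec while its recurrence bullet says 500 or more, so the strict same-severity overlap is above 500 msec.

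**Step 2. Dose path** for a patient with no other reduction, using Table 4.

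- Section 6.2.1: 125 → 100 mg (first event) → 75 mg (recurrence). This is reduction number 2.
- Table 5: 125 → 100 mg (first event) → stop.

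Monitor approval starts at reduction number 3 (50 mg), so the Section 6.2.1 path passes without it. For a patient who had already been reduced once for another reason, the recurrence step would be the third reduction and approval would apply.

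**Step 3. Text that might settle precedence.**

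- *Worst preceding toxicity* (Section 6.2.1 and the Table 5 footer): this cannot decide a same-grade recurrence, because the worst grade has not changed.
- *Section 6.2.1, restart after a delay of more than 14 days*: this requires that "the delay was not due to an AE that requires permanent study drug discontinuation as provided in Table 5". It recognizes Table 5 stops, but only for that restart.
- *Section 6.2.2* sends diarrhea dose modifications to Table 5 as further guidelines. *Section 6.3.1* speaks of interrupting or reducing by Table 5 and does not mention stopping.
- *Section 6.2.3* says that stopping rules exist, without ranking them.
- *Section 7.1.4* requires discontinuation for adverse events that substantially change individual risk-benefit. A second QTcF event could meet this, but that is a judgement, and the list does not name these two Table 5 stops.
- *SAP Section 2.4* classifies deviations and does not say which rule is the withdrawal criterion.

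None of these gives Table 5 precedence for a same-grade recurrence.

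**Step 4. Recurrence at a worse grade.** Where a recurrence reaches a stop grade (for example Grade 2 hypercalcemia returning at Grade 3), the worst-toxicity rule already points to the stop row. These cases are loose wording and are not counted as conflicts. The same-dose sentence does not reach either conflict in Step 1, because both rows resume at a lower dose.

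**The case against.** The best defense is that Section 6.2.1 is a general default and Table 5 holds its exceptions. Section 6.2.1 says *should*, whereas the QTcF row says *will* and the diarrhea row is a direct instruction. Each stop carries a narrower condition (after one reduction; despite optimal treatment). A site reaches the lower dose only by using the Table 5 row, and that row contains the recurrence stop. The cross-references for diarrhea lead to Table 5. Section 6.3.2 also reports preliminary data showing no effect on ECG intervals, so the QTcF case may be rare; the documents give no frequency for either recurrence.

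Most of this stands. It makes Table 5 the likely intended rule and the one most sites would follow. It does not remove the conflict, because the precedence remains an inference in a section that wrote a Table 5 exception for one situation and not for this one.

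A reader might go further and infer that the protocol directs sites to keep dosing after a second serious QTcF event, or that every worse-grade recurrence is another contradiction. The documents do not support either. Table 5 states the QTcF stop in mandatory terms, and the worst-toxicity rule covers recurrences that reach a stop grade.

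**Conclusion.** The inconsistency is real and minor. It affects two Table 5 rows, and the difference is 75 mg against stopping for a patient with no other reduction. It rests on reading the second-reduction sentence as written, without an implied exception, and on the absence of any precedence statement in the sections checked. Grade 3 lipase/amylase should not be added to the count: its hold-and-discuss step departs from Section 6.2.1 but leaves continuation open. Grade 3 diarrhea that recurs without optimal antidiarrheal treatment is also outside the conflict and stays under the second-reduction rule. Nothing here bears on ORR, data collection or any planned analysis. The case for correcting it is patient safety and uniform conduct at very low cost.

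**What to change.** At the next amendment, extend the lower-dose recurrence sentence in Section 6.2.1 with: *unless Table 5 requires discontinuation, in which case study drug is permanently discontinued*. This resolves both conflicts and makes no instruction less cautious. Adding the same clause to the same-dose sentence is optional tidying for recurrences that reach a stop grade.

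A wider exception, such as one yielding to any other action in Table 5, should be avoided. It could let the maintain-dose instructions for Grade 3 neutropenia or fatigue that resolves within 7 days override the reduction required on recurrence.

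The cost is one clause in one sentence (two if the optional edit is made), in a written amendment with the approvals that Section 12.1 requires. Data collection, the SAP and the analysis are unchanged.
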